Critical Gaps in Knowledge. Despite CES' potential for use in first responders, there are no studies that evaluate if a predefined four-week course of CES is feasible and acceptable in firefighters. Although one study examined CES in a sample of 86 first responders consisting mainly of law enforcement as well as 10 firefighters, participants were "permitted to use the device any time of day and for any indication" [c.f. 17] and the report does not mention of how often, at what time of day, and for how long participants used the device or whether

there were difficulties with its use, providing no information about feasibility or acceptability. This is important because it is advised to avoid the use of heavy machinery after CES. Therefore, the application of CES should be carefully integrated with the firefighter work schedules, starting with its use only on off-duty days.

Additionally, there are no studies that test the effects of CES on subjective and objective indices of homeostatic functioning in active-duty firefighters to gain insight into possible mechanisms of CES-modulatory effects. In fact, despite a literature on effectiveness for anxiety, insomnia, and depression [but see 18 for a negative randomized controlled trial], the mechanism of CES effects on homeostatic functioning remains rather hypothetical with little direct evidence [19].

Here we propose to address these critical gaps in science by testing if a course of four weeks of CES in firefighters is 1) feasible and acceptable in this population; 2) impacts subjective variables associated with homeostasis, including fatigue, frequency and intensity of negative and positive emotions (i.e., distressed, nervous, calm, inspired); and 3) changes objective variables associated with homeostasis, including functional and structural neural connectivity, heart rate variability, and sleep quality in a subset of participants.

C. Experimental Method

C1. Brief Description of Subjects

Participants will be 20 active-duty firefighters in the State of Rhode Island, between 18-56 years old.

Participants will be of any racial or ethnic group and of any gender.

C2. Study Design

This study will use a within-subject design, with all participants completing all experimental procedures with no difference to how CES will be applied. Recruitment of 20 participants incorporates an estimated 20% attrition to allow data collection on 16 participants.

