During Visit 2 (prior to four weeks CES) and Visit 3 (post four weeks CES), participants may undergo MRI scanning at the MRI Research Facility (MRF) at Brown University. These visits are optional and participants whose schedule does not allow to complete scanning during available hours at the MRF or who are not MRI eligible will not be excluded for these reasons (this will not hurt the goal of the study which is mainly to test feasibility and acceptability of CES use in this participant population). They will be required to sign a separate MRI consent form at the Brown Facility. When arriving at the facility the first 15 minutes will be used for familiarization with imaging procedures, safety assessment (if using nicotine products participants will be reminded that nicotine patches will need to be removed prior to MRI assessment), and participant placement in the scanner bore. In the scanner, foam wedges will be used to stabilize the participant's head to minimize motion artifact, and a cushion will be placed under the knees for additional comfort. This will be followed by a high-resolution multiecho MPRAGE structural scan. We will use multi-band echo-planar imaging to acquire Blood Oxygen Level Dependent (BOLD) fMRI resting state data. Two 12-minute scans will be obtained in phase encoding directions (A-P;P-A) to reduce field susceptibility bias while participants fixate on a crosshair rendered on a black screen. Additionally, we will collect diffusion tensor imagine data to further improve our understanding of possible neural network changes due to CES.

During Visit 4, at Butler Hospital, participants will complete repeat self-report measures from Visit 1 (e.g., PTSD, depression, anxiety, subjective quality of sleep) to assess potential effects of CES, a debriefing about subjective experiences with CES, the EMA protocol, and Oura ring if applicable.

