The Project Leaders of this supplement, [REDACTED] will be responsible for and supervise data collection and data management. The main goals of this study involve assessing feasibility (i.e., > 75% of CES sessions completed) and acceptability (i.e., < 20% attrition in the sample) of a 4-week course of CES in active-duty firefighters (i.e., at least 16 out of 20 firefighters complete at least 15 out of 20 sessions over four weeks) and obtaining preliminary signal of effect to inform the design of a future, collaborative clinical trial to test efficacy of CES for the prevention of PTSD in first responders. Our primary outcome measures include the number of completed sessions to quantify feasibility and attrition in the sample assessing acceptability (Aim 1). In addition, we will collect data on subjective fatigue, negative and positive emotions using ecological momentary assessment (Aim 2) as well as heart rate variability and sleep quality (Aim 3). Finally, we will collect pre- and post-CES data on clinical symptoms (PTSD, depression, anxiety) and MRI-based resting state functional connectivity and structural connectivity (Aim 3). Given the preliminary nature, the proposed study is not designed to have adequate power to robustly test whether CES is effective for PTSD prevention, which would constitute the long-term goal of the proposed work. As such the proposed number of 20 individuals is solely meant to achieve the listed aims.

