Data will be analyzed through t-tests and general linear models (e.g., (M)AN(C)OVA, repeated measures analyses, linear mixed models) using statistical software (e.g., SPSS, R, MPlus). To maintain anonymity in data files participants will only be listed with their unique identification code. Data backup of these files and hard copies of data capture forms will be kept in locked files to which only authorized study personnel will have access. Descriptive data will be provided for all participants (e.g., mean age, sex, education, etc.). Clinical rating scales will be scored as they are in clinical use. Interpretation of results will adjust for multiple testing to account for false discovery rates using step-down procedures where appropriate [87, 88]. EMA data will be aligned through a timestamp, permitting time parameterization of statistical models. Oura ring data is preprocessed by internal Oura algorithms (e.g., average HRV, Sleep score: REM, latency, deep sleep, restfulness) for comparison over time. All data will be examined for patterns and mechanisms of missingness prior to analyses to ensure missing data approaches are appropriate. For EMA data, we will use Blimp 2.1 to conduct multiple imputation for multilevel missing data prior to analyses. Multiple imputation using a Bayesian estimation approach or via full information maximum likelihood will be implemented as necessary for non-ecological data.

Electronic and/or digitized data (including PHI) will be stored on a password-protected server at Butler Hospital (e.g., COBRE), at the University of Rhode Island, and in CNE REDCap. This study will use Care New England's instance of REDCap for collection and storage of data. The study will not collect or store any actual data within REDCap until the project has been moved into REDCap's production environment. REDCap is a secure, web-based application developed by Vanderbilt University for building and managing surveys and databases. It is primarily designed to support online or offline data capture for research studies, quality improvement, and operations. REDCap provides easy data manipulation (with audit trails for reporting, monitoring and querying patient records), real-time data entry validation, and an automated export mechanism to common statistical packages. When data is downloaded, PHI will be removed and only an assigned code number will remain for analysis.

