- (8) Inconvenience and burden of required time/travel: Travel to Butler Hospital and/or the Brown MRI Research Facility may represent an inconvenience.
- (9) Other: There may be other risks not currently known. For example, participation in this study includes possible worsening of clinical symptoms.

D. Protection of the Subject

D1. Measures to Minimize Potential Risks

- (1) Breach of Confidentiality: Breach of confidentiality is highly unlikely because all data are identified only by numeric code and are stored in locked file cabinets in a locked office in an access-restricted building. A master list of names and numbers is kept in a location separate from all other study data. Only senior research staff will have access to the master list linking names and code numbers. All staff is, or will be, fully trained in relevant ethical principles and procedures, particularly around confidentiality. No personal participant information will be presented in any publication or presentations resulting from this research.
- (2) Distress due to assessment procedures: To minimize the risk of distress arising from assessment procedures (interview and questionnaires), only study staff that has been adequately trained in the assessment battery will complete all assessments. Participants will also be advised that they may choose not to answer any questions that they find upsetting.
- (3) Perception of coercion to participate in the study: To minimize risk of coercion, standard procedures will be followed in obtaining written informed consent. The voluntary nature of participation will be emphasized. Risks and benefits of participation will be explained, along with the rights of the

participant, including the right to withdraw from the study at any time. Additionally, participants will be informed that should they choose to withdraw from the study, this will in no way affect the care they receive at Butler Hospital or their right to participate in future research studies.

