- (5) CES: To minimize risks due to CES, all participants will be carefully screened for contraindications to CES as listed in the exclusion criteria. As the risks of CES during pregnancy are unknown (although most likely not harmful), pregnant individuals are excluded from participation based on historical guidelines. Use of an electrically isolated power source (i.e., battery-powered stimulation device) also protects against delivery of more intense currents than intended. Stimulation parameters (current and frequency) will be preset and tested for tolerability during Visit 1 under the guidance of Drs. [REDACTED] [REDACTED]. Participants will be told that modification of the Alpha-Stim device or accessories is not allowed, and that doing so could result in injury. They will also be told to not stimulate directly on the eyes or press the probes over the carotid sinus (on the neck near the larynx) and application of the electrodes near the thorax may increase the risk of cardiac fibrillation, as well as that it is advised to not use dangerous machinery or vehicles during treatment days, and that for that reason CES should only be applied/used on off-duty days or after completion of a duty cycle. Participants will have the option of discontinuing the study at any time and will be explicitly instructed to contact the research team if they experience any discomfort. The research team will reach out to participants at least once per week during the four weeks of CES (or more often if indicated based on incomplete EMA surveys or difficulties using the CES device). To assess for presence of adverse events, we will use a recently adapted Side Effects Questionnaire based on the one developed by Brunoni and colleagues [26]. If there is any doubt about the mental or physical status of an individual during the CES intervention, participants will be evaluated by Dr. [REDACTED] in her role as clinical psychologist, who will make recommendations for follow-up care, if required. Telephone or in-person follow-up will be arranged as needed and will not be considered a protocol deviation. Any participant judged on clinical grounds to have suffered adverse effects will thus be evaluated and treated as necessary and withdrawn from the study if deemed necessary.

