[REDACTED] have extensive experience conducting non-invasive neuromodulation in individuals presenting with a variety of (sub)clinical psychiatric symptoms, including anxiety, posttraumatic stress, and depression. Specifically, Drs. [REDACTED] have ongoing projects utilizing electrical current stimulation supported by the COBRE Center for Neuromodulation project and which are performed at Butler's Neuromodulation Research Facility. Dr. [REDACTED], as a clinical psychologist and Director of the Study of Trauma, Risk-taking, Emotions, and Stress Symptoms (STRESS) Lab, has substantial background in the pathogenesis of posttraumatic stress disorder. Likewise, [REDACTED] projects mainly involve the use of non-invasive brain stimulation techniques in individuals with posttraumatic stress disorder. All participants will be carefully screened prior to study entry, and the application of and device settings for CES will be

practiced and set prior to providing the CES device to participants. Other participant safeguards with respect to study procedures are described in Protection of Human Subjects. A member of the research team will be available during working hours, and the research team will check-in with participants at least once a week. In the event of any adverse event, Dr. [REDACTED] as study PI will be contacted to facilitate subsequent assessment and treatment or referral as necessary.

In the event of any participant becoming unstable or demonstrating worsening of clinical symptoms during the study duration, study procedures will be stopped for this individual and Dr. [REDACTED] as study PI will be contacted and she will follow-up with Drs. [REDACTED] in their role as clinical psychologist as well as the on-call physician at the Butler Hospital TMS Clinic. In case, Dr. [REDACTED] is not available, the on-call physician at the Butler Hospital TMS Clinic will be contacted to facilitate treatment or referral. In case of emergency medical assistance, the study team will contact 911 and/or the Brown University EMS response team depending on severity and location (e.g., while at the Brown University MRI Research Facility). All research staff as well as MRI facility staff members at the Brown University MRI Research Facility are trained in basic first aid, CPR, and MRI safety and evacuation protocols.

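### The stop-on-worsening rule halts all study procedures and does not say whether the post-CES symptom scales are still collected, so the pre/post signal may tilt toward improvement

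*Combined protocol and SAP*

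**What the plan says.** Worsening is an anticipated event. Section C, Potential Risks, item (9) states that "participation in this study includes possible worsening of clinical symptoms". The response is in D3, Data Safety Monitoring Plan: for a participant who becomes unstable or is "demonstrating worsening of clinical symptoms during the study duration, study procedures will be stopped for this individual". No severity threshold is given, and no exception is made for outcome assessment.

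D1, item (5) adds clinical handling. "Telephone or in-person follow-up will be arranged as needed and will not be considered a protocol deviation", and a participant judged to have suffered adverse effects is "evaluated and treated as necessary and withdrawn from the study if deemed necessary". No outcome scale is mentioned there.

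The symptom scales are taken at Visit 1 and once more at Visit 4, where "participants will complete repeat self-report measures from Visit 1" (C3). C2 says that every participant completes the last visit, and D1, item (9) says that staff evaluate participants before and after CES. Neither mentions participants who have been stopped.

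C4 makes sessions completed and attrition the primary outcomes. It also lists "obtaining preliminary signal of effect to inform the design of a future, collaborative clinical trial" among the main goals. For missing data outside EMA it plans a check of missingness patterns and then: "Multiple imputation using a Bayesian estimation approach or via full information maximum likelihood will be implemented as necessary for non-ecological data".

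**The concern.** The trigger for stopping is closely related to what the scales measure. Ordinary dropout may or may not be related to outcome. Loss caused by this rule is related to it by construction, and in a known direction: those who got worse are the ones without a second score. With one arm and a before/after comparison, there is no control group in which the same loss could offset it.

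At stake is the preliminary symptom signal that the study hands to the next trial. If those who worsen drop out of the post-CES mean, CES looks somewhat more helpful, or less harmful, than it was. A score never collected cannot be recovered at analysis. It can only be modelled.

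**Working it through.** **The plan's own figure.** C2 states: "Recruitment of 20 participants incorporates an estimated 20% attrition to allow data collection on 16 participants". Check: 16 / (1 - 0.20) = 20, and 20 x 0.80 = 16. It reproduces. The plan gives no SD, effect size or rate of worsening for the symptom scales, so everything below is illustration on stated assumptions.

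**Assumptions.** n = 20. Change scores are standard normal (SD of change = 1, positive = worse) and the true mean change is 0. The k participants with the highest worsening signal are stopped and lose the Visit 4 score. The signal correlates r with the final change, with r from 0.5 to 1. Analysis is of completers only, which is not an analysis the plan names.

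**Formula.** Let S(k) be the expected sum of the k largest of 20 standard normal values. All 20 average zero, so the expected completer mean is -r x S(k) / (20 - k). Numerical integration gives S(1) = 1.867, S(2) = 3.275 and S(4) = 5.327.

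- k = 1: 1.867 / 19 = 0.098 at r = 1, and half that, 0.049, at r = 0.5.
- k = 2: 3.275 / 18 = 0.182 and 0.091.
- k = 4: 5.327 / 16 = 0.333 and 0.166.

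Simulation (100,000 replicates) agrees and adds the rejection rate of a two-sided 5% t-test:

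| Stopped, of 20 | Spurious improvement (SD), r = 0.5 to 1 | Two-sided rejection |
|---|---|---|
| 0 | 0 | 5% |
| 1 | 0.05-0.10 | 6-9% |
| 2 | 0.09-0.18 | 7-16% |
| 4 (upper bound) | 0.17-0.33 | 11-38% |

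The last row uses the whole any-cause attrition allowance for worsening alone, so it is a ceiling and not an expectation. If 4 of 20 are lost but only 1 or 2 because of worsening, the shifts are essentially the same and rejection is 6-8% or 7-15%. For scale, the standard error of the mean change is 1 / sqrt(20) = 0.22 SD.

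**Would the planned missing-data methods remove it?** Likelihood estimation from the baseline score alone barely helps. At r = 1, with a pre/post correlation of 0.5 to 0.8, 0.15-0.17 of the 0.18 SD remains with 2 stops. Adding EMA recorded before the stop as a predictor helps according to how well it tracks the stopping signal (ranges are r = 0.5 to 1):

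| EMA-signal correlation | 1 stop | 2 stops |
|---|---|---|
| 0.5 | 0.04-0.08 SD | 0.07-0.15 SD |
| 0.8 | 0.02-0.04 SD | 0.04-0.08 SD |
| 0.95 | about 0.01 SD or less | 0.01-0.02 SD |

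The methods in C4 can therefore remove most of the shift, but only if EMA captures the trigger and is put in the model.

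**Would collecting the score remove it?** With 2 stops and 1 score recovered, 0.04-0.10 SD remains, or 0.07-0.13 SD if care after the stop improves that score by 0.5 SD. With both recovered and the same care effect, 2 x 0.5 / 20 = 0.05 SD remains. With a 1 SD care effect the residual is 2 x 1 / 20 = 0.10 SD, no better than the 0.09 SD from doing nothing at r = 0.5.

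**The case against.** The strongest reply is that the protocol does not cancel Visit 4. C2 has everyone completing the last visit. D1, item (9), the measure paired with the risk of worsening, promises a post-CES evaluation and a psychologist's judgement on whether continuing is safe and reasonable. D1, item (5) makes withdrawal discretionary. A fair joint reading is stop, evaluate, then decide, in which case a stop may be temporary and nothing is lost.

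This stands in part. A reader might infer that the plan discards the scores of everyone who worsens. The documents do not support that, because they leave the point open. Equally, they do not settle it the other way. The C2 sentence mainly contrasts the last visit with the optional MRI visits, and D1, item (9) names neither the scales nor stopped participants.

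The second reply is that worsening must be seen before it can trigger a stop. Since the scales are taken only at Visits 1 and 4, it would be seen largely through EMA or weekly check-ins. Much of the trigger may then be recorded data, and worsening first found at Visit 4 loses nothing. That is also right as far as it goes, and it is why the residual can fall to 0.02 SD or below. But C4 does not name EMA as a predictor for the scale data.

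Third, the effect is small. Stops may be few or none, given the psychiatric and medical exclusions and the side-effect rate below 1% cited in the risk section. One or two stops shift the mean by less than its standard error, and the study says that it is not powered to test effectiveness. This stands and sets the severity.

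Finally, halting everything for an unstable participant is a legitimate safety choice, and the protocol itself notes that rating scales can distress. The fix leaves that judgement with the clinician.

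**Conclusion.** The point holds, conditionally, and is minor. If the D3 rule is applied literally and the stop is permanent, participants who worsen lose their only post-CES symptom and sleep scores, and the non-primary pre/post signal may shift toward improvement. The illustrated size is 0.05-0.10 SD with one stop and 0.09-0.18 SD with two, in a completers-only analysis with no true effect. It is zero with no stops, and about 0.00-0.02 SD if EMA tracks the trigger at 0.95 and is used in the model. The number of stops, the correlations and the SD scale are assumptions, because the documents give none.

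Two stronger inferences should be resisted. Aim 1 is not biased toward success: a stopped participant would be expected to count as attrition, and D3 tracks adverse events and withdrawals. Nor is any direction of bias established for the MRI measures.

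**What to change.** Amend the D3 sentence so that worsening stops CES, while the Visit 4 self-report scales are still offered, remotely if needed, when the participant agrees and the responsible clinician does not object. The clinical threshold for stopping stays with the investigators. Count these participants as attrition in Aim 1 and include their Visit 4 scores in the pre/post analysis. Report the number stopped, the number with no post score, and care received between the stop and the score. Section 3A already provides for recording ongoing medical care.

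Optionally, name pre-stop EMA as an auxiliary variable in the C4 missing-data plan and add a sensitivity analysis that assigns the worst observed change to missing post scores.

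The cost is one protocol sentence and a few reported counts, with no new visit or instrument. The downside is brief extra contact that a few stopped participants may find distressing, and scores that may partly reflect care received after the stop. The bias is reduced, but its removal is not guaranteed, which is why the later care needs to be reported.
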